8.3. Lost to Follow-up

A participant will be considered lost to follow-up if he/she repeatedly fails to return for scheduled visits and is unable to be contacted by the study site.

The following actions must be taken if a participant fails to return to the clinic for a required study visit:

- The site must attempt to contact the participant and reschedule the missed visit as soon as possible, counsel the participant on the importance of maintaining the assigned visit schedule and ascertain whether the participant wishes to and/or should continue in the study.
- Before a participant is deemed lost to follow-up, the investigator or designee must make every effort to regain contact with the participant (where possible, three telephone calls, and if necessary, a certified letter to the participant's last known mailing address or local equivalent methods). These contact attempts should be documented in the participant's medical record.
- Should the participant continue to be unreachable, he/she will be considered to have withdrawn from the study.

- Site personnel, or an independent third party, will attempt to collect the vital status of the participant within legal and ethical boundaries for all participants randomized, including those who did not get study intervention. Public sources may be searched for vital status information. If vital status is determined as deceased, this will be documented, and the participant will not be considered lost to follow-up. Sponsor personnel will not be involved in any attempts to collect vital status information.

9. Study Assessments and Procedures

Study procedures and their timing are summarized in the SoA. Protocol waivers or exemptions are not allowed.

- Immediate safety concerns should be discussed with the sponsor immediately upon occurrence or awareness to determine if the participant should continue or discontinue study intervention.
- Adherence to the study design requirements, including those specified in the SoA, is essential and required for study conduct.
- All screening evaluations must be completed and reviewed to confirm that potential participants meet all eligibility criteria. The investigator will maintain a screening log to record details of all participants screened and to confirm eligibility or record reasons for screening failure, as applicable.
- Procedures conducted as part of the participant's routine clinical management (e.g., blood count) and obtained before signing of the ICF may be utilized for screening or baseline purposes provided the procedures met the protocol-specified criteria and were performed within the timeframe defined in the SoA.
- Safety/laboratory results that could unblind the study will not be reported to investigative sites or other blinded personnel until the study has been unblinded.

The maximum amount of blood collected from each participant over the duration of the study, including any extra assessments that may be required, will be outlined in the ICF. Repeat or unscheduled samples may be taken for safety reasons or for technical issues with the samples.

9.1. Efficacy Assessments

Planned timepoints for all efficacy assessments are provided in the SoA (Section 1.3).

9.1.1. Movement Disorder Society-Unified Parkinson's Disease Rating Scale (MDS-UPDRS)

The MDS-UPDRS is a well-established tool for characterizing the signs and symptoms of PD (Goetz et al, 2008). The three parts used in this study are: Part I (Non-Motor Aspect of

Experiences of Daily Living), Part II (Motor Aspects of Experiences of Daily Living), and Part III (Motor Examination). Items in each domain are rated from 0-4, where 0 = normal, 1 = slight, 2 = mild, 3 = moderate, and 4 = severe.

9.1.2. Patient Global Impression – Severity (PGI-S)

The PGI-S is a single-item tool used to determine how severe a person feels their symptoms are at the time of questioning. It is based on a 5-point scale (None, mild, moderate, severe, very severe).

9.1.3. Clinician Global Impression of Severity (CGI-S)

The CGI-S is a 7-point scale used to indicate how the clinician views the severity of the patients illness at the time of questioning (Guy, 1976). The range includes 1 (“normal”), 2 (“borderline ill, not ill at all”), 3 (“mildly ill”), 4 (“moderately ill”), 5 (“markedly ill”), 6 (“severely ill”), and 7 (“among the most extremely ill patients”).

9.1.4. Parkinson’s Disease Questionnaire (PDQ-39)

The PDQ-39 is a self-administered questionnaire that assesses how often people affected by PD experience difficulties across 8 dimensions of daily living, including mobility (10 items), activities of daily living (6 items), emotional well-being (6 items), stigma (4 items), social support (3 items), cognition (4 items), communication (3 items), and bodily discomfort (3 items). (Peto et al 1995). It also assesses the impact of PD on specific dimensions of functioning and well-being. The PDQ-39 is scored on a scale of 0 to 100, with lower scores indicating better health and higher scores more severe symptoms.

9.1.5. Schwab and England Activities of Daily Living Scale (SE-ADL)

The SE-ADL is a single item that assesses the difficulty that a patient has in completing daily activities. It ranges from 0% (bedridden) to 100% (completely independent). Scores are coded in increments of 10 (i.e., 100, 90, 80, 70, ...). The rater column does not need to be completed.

9.1.6. Non-Motor Symptom Scale (NMSS)

The NMSS is a 30-item scale divided into 9 domains (cardiovascular, sleep/fatigue, mood/cognition, perceptual problems/hallucinations, attention/memory, GI, urinary, sexual function, miscellaneous) (Chaudhuri et al 2007). Each item is rated for frequency (rarely/often/frequent/very frequent) and severity (none/mild/moderate/severe) of symptoms.

9.1.7. Complete Spontaneous Bowel Movement Score (CSBM)

The total number of spontaneous bowel movements and the stool types will be assessed at baseline, week 4, week 8, and week 12. A patient diary will be provided to record all bowel movements in the 7 days leading up to these timepoints. A spontaneous bowel movement is a stool not induced by rescue medication such as laxative, enema, or suppository use during the previous 24 hour period. “Complete” refers to the sensation of complete evacuation of the stool (Lacy et al, 2012).

9.1.8. Patient Assessment of Upper GI Disorders Severity Index (PAGI-SYM)

The PAGI-SYM measures symptom severity in patients with upper GI disorders. The patient is asked to rate the severity of symptoms over the last 2 weeks. There are 20 items which are rated from 0 (none) to 5 (very severe).

9.1.9. Patient Assessment of Constipation Quality of Life (PAC-QoL)

The PAC-QoL assesses the effect that constipation has on daily life over the past 2 weeks. There are 28 items which are rated from 0 (not at all) to 4 (extremely).

9.1.10. Patient Assessment of GI Disorders Severity Quality of Life (PAGI-QoL)

The PAGI-QoL assesses the effect that GI problems have on daily life over the past 2 weeks. There are 30 items which are rated from 0 (none of the time) to 5 (all the time).

9.1.11. Epworth Sleepiness Scale (ESS)

The ESS assesses sleepiness over time. Patients and Caregivers are asked to rate (on a scale of 0 to 3) their likelihood of falling asleep during 8 daily activities, including reading, watching television, and driving.

9.2. Safety Assessments

Planned timepoints for all safety assessments are provided in the SoA (Section 1.3).

9.2.1. Physical Examinations

A complete physical examination will include, at a minimum, assessments of the cardiovascular, respiratory, lymphatic, musculoskeletal, GI, and neurological systems as well as assessment of general appearance, abdomen, skin, and extremities. Height and weight will also be measured and recorded.

9.2.2. Vital Signs

Vital signs (VS) for blood pressure and pulse are to be measured after subjects remain supine for 5 min and after 2 min standing. Baseline VS will be measured 3 times at baseline over the course of an hour. Respiratory rate, pulse oximetry and temperature will also be collected. Vital signs measurements outside of the normal range (as per the CRU SOP) should be repeated. All time points are relative to the time of dosing.

9.2.3. Electrocardiograms

Standard (triplicate) 12-lead ECG(s) will be obtained as outlined in the SoA (see Section 1.3) using an ECG machine that automatically calculates the heart rate and measures PR, QRS, QT, and QTc intervals. Corrected QT interval should be done by Fredericia (QTcF).

9.2.4. Clinical Safety Laboratory Tests

See Appendix 2 for the list of clinical laboratory tests to be performed and the SoA (Section 1.3) for the timing and frequency.

The investigator must review the laboratory report, document this review, and record any clinically significant changes occurring during the study as an AE. The laboratory reports must be filed with the source documents.

Abnormal laboratory findings associated with the underlying disease are not considered clinically significant unless judged by the investigator to be more severe than expected for the participant's condition.

All laboratory tests with values considered clinically significantly abnormal during participation in the study or within 30 days after the last dose of study intervention should be repeated until the values return to normal or baseline or are no longer considered clinically significant by the investigator or medical monitor.

- If clinically significant values do not return to normal/baseline within a period of time judged reasonable by the investigator, the etiology should be identified, and the sponsor should be notified.
- All protocol-required laboratory tests, as defined in Appendix 2, must be conducted in accordance with the laboratory manual and the SoA (Section 1.3).

- If laboratory values from non-protocol-specified laboratory tests performed at the institution's local laboratory require a change in participant management or are considered clinically significant by the investigator (e.g., SAE or AE or dose modification), then the results must be recorded.

9.2.5. Pregnancy Testing

All women of childbearing potential will take serum/urine pregnancy tests, per SoA (Section 1.3).

9.2.6. Ophthalmic Exams

Ophthalmic exams include:

- Best corrected visual acuity
- Slit lamp examination of the anterior segment, particularly cornea, aqueous and lens. Slit lamp examination should determine the potential presence of dry eye, inflammatory cells in the aqueous and lens opacities.
- Wide-field photography
- Wide-field autofluorescence
- Wide-field fluorescein angiography (WF-FA)
- Spectral domain optical coherence tomography (SD-OCT)

Ophthalmic exams are performed at screening and at 12 weeks. All images will be uploaded to a secure portal with patient-identifying information redacted. Exam reports are required for all ophthalmic exams at screening and at 12 weeks. The exam reports at 12 weeks must compare observations at 12 weeks to what was observed at screening to determine if any changes occurred.

9.2.7. Pharmacokinetics

Blood samples will be drawn either *pre-dose (at baseline) or either pre-dose or post-dose* on the subsequent visit days (see SoA) to analyze steady-state pharmacokinetics for IkT-148009 and its primary metabolites.

9.2.8. Suicidal Ideation and Behavior Risk Monitoring

Patients with PD may occasionally develop suicidal ideation or behavior.

Participants being treated with IkT-148009 should be monitored appropriately and observed closely for suicidal ideation and behavior (SIB) or any other unusual changes in behavior throughout the study. Participants who experience signs of SIB should undergo a risk assessment.

All factors contributing to SIB should be evaluated and consideration should be given to discontinuation of the study intervention.

During the informed consent process, families and caregivers of participants being treated with IkT-148009 should be alerted about the need to monitor participants for the emergence of SIB and to report such symptoms immediately to the study investigator.

Baseline assessment of SIB/intervention-emergent SIB will be monitored throughout the study period using the C-SSRS. The C-SSRS will be assessed by trained personnel only. The scale consists of 4 categories: suicidal ideation, intensity of suicidal ideation, suicidal behavior, and actual/potential lethality which can be answered by Yes or No. At the screening visit the questionnaire for the past 6 months will be used, and for all other visits the version “Since the last visit” will be administered.

At each suicidality assessment, participants thought to have significant suicidal ideation with actual plan and intent or suicidal behavior must be evaluated by a clinician or mental health professional skilled in the evaluation of suicidality, who will determine if it is safe for the participant to continue in the trial. Specific criteria that indicate a need for further assessment include:

- Suicidal ideation associated with actual intent and/or plan in the past 6 months; (a “YES” answer to C-SSRS questions 4 “some intent to act without specific plan” or 5 “specific plan and intent”).
- Previous history of suicide behaviors in the past 5 years (a “YES” answer to any of the suicidal behavior items of the C-SSRS with the behavior occurring in the past 5 years).
- The investigator’s judgment that a risk assessment is warranted.

Participants who respond “Yes” to items 4 or 5, or to any behavioral question of the C-SSRS on more than one occasion during the trial may be discontinued from the trial.

9.3. Adverse Events (AEs) Serious Adverse Events (SAEs), and Other Safety Reporting

The definitions of AEs and SAEs can be found in Appendix 3.

AEs will be reported by the participant (or, when appropriate, by a caregiver, surrogate, or the participant’s legally authorized representative [LAR]).

The investigator and any qualified designees are responsible for detecting, documenting, and recording events that meet the definition of an AE or SAE and remain responsible for following up AEs that are serious, considered related to the study intervention or study procedures, or that caused the participant to discontinue the study intervention/study.

The method of recording, evaluating, and assessing causality of AEs and SAEs and the procedures for completing and transmitting SAE reports are provided in Appendix 3.

9.3.1. Time Period and Frequency for Collecting AE and SAE Information

All SAEs will be collected from the signing of the ICF until the follow-up visit at the timepoints specified in the SoA (Section 1.3).

All AEs will be collected from the signing of the ICF until the follow-up visit at the timepoints specified in the SoA (Section 1.3).

During the screening period baseline abnormalities (any sign or symptom present, such as abnormal screening laboratory value) will be assessed for clinical significance and captured in medical history as ongoing. Any baseline abnormality that increases in severity or frequency should be captured as an adverse event if determined clinically significant by the investigator. All SAEs will be recorded and reported to the sponsor or designee immediately and under no circumstance should this exceed 24 hours, as indicated in Appendix 3. The investigator will submit any updated SAE data to the sponsor within 24 hours of it being available.

Investigators are not obligated to actively seek information on AEs or SAEs after conclusion of the study participation. However, if the investigator learns of any SAE, including a death, at any time after a participant has been discharged from the study, and he/she considers the event to be reasonably related to the study intervention or study participation, the investigator must promptly notify the sponsor.

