10.3.1. Definition of AE

AE Definition

 • An AE is any untoward medical occurrence in a clinical study participant, temporally associated with the use of study intervention, whether or not considered related to the study intervention. • NOTE: An AE can therefore be any unfavorable and unintended sign (including an abnormal laboratory finding), symptom, or disease (new or exacerbated) temporally associated with the use of study intervention.
Definition of Unsolicited and Solicited AE

 • An unsolicited adverse event is an adverse event that was not solicited using a participant diary and that is communicated by a participant/participant's parent(s)/LAR(s) who has signed the informed consent. Unsolicited AEs include serious and non-serious AEs. • Potential unsolicited AEs may be medically attended (i.e., symptoms or illnesses requiring a hospitalization, emergency room visit, or visit to/by a healthcare provider). The participants/participant's parent(s)/LAR(s) will be instructed to contact the site as soon as possible to report medically attended event(s), as well as any events that, though not medically attended, are of participant/participant's parent(s)/LAR(s) concern. Detailed information about reported unsolicited AEs will be collected by qualified site personnel and documented in the participant's records. • Unsolicited AEs that are not medically attended nor perceived as a concern by the participant/participant's parent(s)/LAR(s) will be collected during an interview with the participants/participant's parent(s)/LAR(s) and by review of available medical records at the next visit.
Events Meeting the AE Definition

 • Any abnormal laboratory test results (hematology, clinical chemistry, or urinalysis) or other safety assessments (e.g., Electrocardiogram [ECG], radiological scans, vital signs measurements), including those that worsen from baseline, considered clinically significant in the medical and scientific judgment of the investigator (i.e., not related to progression of underlying disease) • Exacerbation of a chronic or intermittent pre-existing condition including either an increase in frequency and/or intensity of the condition • New condition detected or diagnosed after study intervention administration even though it may have been present before the start of the study

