- Signs, symptoms, or the clinical sequelae of a suspected intervention-intervention interaction

Events NOT Meeting the AE Definition

- Any clinically significant abnormal laboratory findings or other abnormal safety assessments that are associated with the underlying disease, unless judged by the investigator to be more severe than expected for the participant's condition
- The disease/disorder being studied or expected progression, signs, or symptoms of the disease/disorder being studied, unless more severe than expected for the participant's condition
- Medical or surgical procedure (e.g., endoscopy, appendectomy): the condition that leads to the procedure is the AE
- Situations in which an untoward medical occurrence did not occur (social and/or convenience admission to a hospital)
- Anticipated day-to-day fluctuations of pre-existing disease(s) or condition(s) present or detected at the start of the study that do not worsen

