10.3.3. Recording and Follow-Up of AE and/or SAE

AE and SAE Recording

 • When an AE/SAE occurs, it is the responsibility of the investigator to review all documentation (e.g., hospital progress notes, laboratory reports, and diagnostics reports) related to the event. • The investigator will then record all relevant AE/SAE information. • There may be instances when copies of medical records for certain cases are requested by sponsor/sponsor designee/local health authorities. In this case, all participant identifiers, with the exception of the participant number, will be redacted on the copies of the medical records before submission to sponsor/sponsor designee/local health authorities. • The investigator will attempt to establish a diagnosis of the event based on signs, symptoms, and/or other clinical information. Whenever possible, the diagnosis (not the individual signs/symptoms) will be documented as the AE/SAE.
Assessment of Intensity

The investigator will assess intensity for each AE and SAE reported during the study and assign it to one of the following categories:

- Mild: Asymptomatic or mild symptoms; clinical or diagnostic observations only; intervention not indicated.
- Moderate: Minimal, local, or noninvasive intervention indicated; limiting age-appropriate instrumental Activities of Daily Living (ADL). Instrumental ADL refers to preparing meals, shopping for groceries or clothes, using the telephone, managing money, etc.

- Severe: Severe or medically significant but not immediately life-threatening; hospitalization or prolongation of hospitalization indicated; disabling, limiting self-care ADL. Self-care ADL refers to bathing, dressing, and undressing, feeding self, using the toilet, taking medications, and not bedridden.

Assessment of Causality

- The investigator is obligated to assess the relationship between study intervention and each occurrence of each AE/SAE. The investigator will use clinical judgment to determine the relationship.
- A reasonable possibility of a relationship conveys that there are facts, evidence, and/or arguments to suggest a causal relationship, rather than a relationship cannot be ruled out.
- Alternative causes, such as underlying disease(s), concomitant therapy, and other risk factors, as well as the temporal relationship of the event to study intervention administration, will be considered and investigated.

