#### **3.4.2 Adverse events**

The adverse event verbatim descriptions (investigator terms from the CRF) will be classified into medical terminology using the Medical Dictionary for Regulatory Activities (MedDRA). Adverse events will be coded to primary System Organ Class (SOC) and preferred term (PT) using MedDRA, Version 26.0 or newer.

A treatment-emergent adverse event (TEAE) is defined as an AE that had an onset date, or a worsening in severity from baseline (pre-treatment), on or after the first dose of study intervention up to the Safety follow-up visit or Early Termination Visit following study drug discontinuation.

An AE will be considered treatment related if the investigator considers that there is a reasonable possibility that the event may have been caused by the investigation product. If a causal relationship to study intervention is missing for an AE that started on or after the date of first dose of study intervention, causality will not be imputed and a category of “missing” will be included as necessary in incidence summaries. An event with missing onset date will be imputed as treatment-emergent, unless there is other evidence that confirms that the event was not treatment-emergent (e.g., the event end date was prior to the study intervention start date).

---

An AE will be considered serious (SAE) if it meets the definition of SAE given in the protocol Appendix 10.3.2, as recorded on the AE form of the CRF.

If AE have missing or incomplete start or end dates, they will be imputed as described in [Appendix 8.1](#).

The SOCs will be presented in alphabetical order and the PTs will be presented in frequency order for the highest dose of active treatment within each SOC. A participant who reports more than 1 AE in different SOCs will be counted once in the overall total. A participant who reports AEs in different PTs in the same SOC will be counted only once in the SOC total. A participant reporting more than 1 AE in a given PT will be counted only once for that term. In severity and relatedness tables, the most severe or related AE will be counted.

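### Protocol 9.3.1 ties AE capture of worsened baseline symptoms to investigator-judged clinical significance, a condition Appendix 10.3.1 does not set for pre-existing conditions, so sites following 9.3.1 may under-record mainly mild TEAEs in the primary endpoint.

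*Protocol*

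**What the plan says.** **Capture instruction.** Protocol 9.3.1 takes as its subject "baseline abnormalities (any sign or symptom present, such as abnormal screening laboratory value" and has these entered in medical history. For later worsening it says: "Any baseline abnormality that increases in severity or frequency should be captured as an adverse event if determined clinically significant by the investigator".

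**Definition.** Protocol 9.3 states that "The definitions of AEs and SAEs can be found in Appendix 3" and makes investigators responsible for recording whatever meets them. Under Appendix 10.3.1 the events that count include "Exacerbation of a chronic or intermittent pre-existing condition including either an increase in frequency and/or intensity of the condition". That bullet has no clinical-significance test. The test is in a separate bullet, for laboratory results and other safety assessments such as ECG and vital signs, which count when "considered clinically significant in the medical and scientific judgment of the investigator". The appendix excludes "expected progression, signs, or symptoms of the disease/disorder being studied, unless more severe than expected", and also anticipated fluctuation of an existing condition without worsening.

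**Severity and counting.** The intensity scale in Protocol 10.3.3 begins at "Mild: Asymptomatic or mild symptoms; clinical or diagnostic observations only; intervention not indicated". SAP 3.4.2 defines a TEAE as an AE with onset, "or a worsening in severity from baseline (pre-treatment), on or after the first dose of study intervention". TEAE incidence is the first primary endpoint (Protocol section 3; SAP 1.2.1). Protocol 5.4.5 and SAP 4.3.2 plan no inferential analysis of safety data.

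**The concern.** For one kind of event, a symptom present at screening that gets worse on study, two current sections give sites different instructions. Under the appendix an increase in frequency or intensity is enough. Under 9.3.1 the investigator must also find it clinically significant. No precedence rule between the two is stated, and the protocol allows up to 40 sites.

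The condition falls mainly on mild events, because a worsening that needs no intervention is the kind an investigator is likely to call not significant. A new mild symptom is recorded without that test, while an equally mild worsening of an existing symptom may not be. The SAP cannot restore it, since its TEAE definition starts from events already entered as AEs. At stake are the completeness of the primary endpoint at the mild end and its comparability across sites.

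**Working it through.** The plan states no figure on this point. The safety group size of 30 per dose has no calculation behind it (Protocol 5.6), so there is nothing to reproduce. The main check is a comparison of the texts by type of worsening.

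1. **Laboratory, ECG and vital-sign findings.** 9.3.1 requires clinical significance, and so does the safety-assessment bullet of 10.3.1, including for values that worsen from baseline. No conflict. The one example in 9.3.1, a screening laboratory value, belongs here.
2. **Physical-examination findings.** Protocol 5.4.5 also reports aggravated existing abnormalities as AEs when judged clinically significant. It agrees with 9.3.1.
3. **Expected Parkinson's disease signs, symptoms and progression.** 10.3.1 excludes these unless they are more severe than expected. Aligning 9.3.1 with the appendix would not turn them into AEs.
4. **Symptoms of other pre-existing conditions.** 9.3.1 requires clinical significance; the exacerbation bullet does not. The general AE definition in 10.3.1 also covers exacerbated symptoms. This is where the two rules conflict, and 9.3.1 is the narrower.

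**Size, as illustration.** Let *w* be the true proportion of an arm with a type 4 worsening and *s* the share of those that sites record. Both are assumptions; the documents give neither. The recorded proportion is *s·w*, and the recorded difference between two arms is *s·(w₁ − w₀)* if *s* is the same in both.

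Expected participants recorded among 30, which is 30·*s*·*w*:
- *w* = 0.10: 3.0, 2.25, 1.5 and 0.75 for *s* = 1, 0.75, 0.50 and 0.25.
- *w* = 0.20: 6.0, 4.5, 3.0 and 1.5.
- *w* = 0.40: 12, 9, 6 and 3.

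At *w* = 0.20 the chance of seeing at least 3 such participants in an arm, from a binomial with n = 30 and probability *s·w*, is 0.956, 0.849, 0.589 and 0.188. With *s* = 1 there is no loss.

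For a difference, assume 45% on one dose and 20% on placebo. With *s* = 1, 0.8 and 0.5 the recorded difference is 25, 0.8 × 25 = 20, and 0.5 × 25 = 12.5 percentage points. As a rough yardstick for visibility, at 34 per arm (137/4 = 34.25, from the enrolment in SAP 1.3.1) the chance that a Newcombe 95% interval lies above zero is 0.614, 0.463 and 0.273. The trial plans no such interval.

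**Limit of the scaling.** The multiplier *s* applies to the incidence of these particular events. SAP 3.4.2 counts each participant once in the overall total, so someone with another recorded TEAE still counts. If a share *q* has another TEAE, independently of the worsening, the loss in overall incidence is (1 − *q*)·*w*·(1 − *s*), which is smaller than *w*·(1 − *s*).

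**The case against.** The best defence is that the protocol names its own authority. Section 9.3 sends the reader to Appendix 3 for the definition and requires recording of events that meet it. Section 9.3.1 is headed as a matter of timing and frequency and says that all AEs are collected. It uses the word if, not only if, so it does not forbid recording other worsening. This part stands: it makes the under-count a risk that depends on how sites read the text, not an established fact. It does not remove the conflict, because 9.3.1 tells sites what to capture in exactly this case, and a site that follows it literally can miss events the appendix defines as AEs.

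A reader might infer that Appendix 3 counts every worsening, or that the many non-motor symptoms of Parkinson's disease make the loss large. The documents do not support either. The appendix requires clinical significance for laboratory and other safety assessments, and it excludes expected disease features, which covers many symptoms present at entry.

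The rates used for size are assumed, and a confidence-interval criterion does not match a descriptive safety analysis. That stands too. A common *s* is also a simplification, since larger worsenings may pass a significance judgment more often. Investigators are blinded, and nothing in the documents shows differential capture by arm.

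Finally, moderate or severe events and SAEs should be little affected, and the NMSS, MDS-UPDRS Part I, ESS and gastrointestinal scales measure many baseline symptoms without this filter. This limits the harm, but those scales are secondary endpoints and do not replace the TEAE count.

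**Conclusion.** The inconsistency is real and in current text, but narrow. It concerns symptoms of pre-existing conditions outside the Appendix 3 exclusions. For those, sites that apply 9.3.1 literally may under-record mainly mild worsening, which lowers TEAE incidence and absolute differences between arms in the primary endpoint. The size cannot be fixed from the documents: it runs from no loss, if every such worsening is judged significant, to a reduction in proportion to the share left out. The conclusion that 9.3.1 does under-count the endpoint, or that it biases the comparison of a dose with placebo differently by arm, goes beyond the documents. It remains worth correcting because the rule feeds a primary endpoint and the change is small.

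**What to change.** In Protocol 9.3.1, limit the clinical-significance condition to laboratory, ECG, vital-sign and examination findings, in line with Appendix 10.3.1 and Protocol 5.4.5. For increased severity or frequency of a symptom of a pre-existing condition, refer to 10.3.1 and have it graded under 10.3.3. Leave the 10.3.1 exclusions as they are, and carry the same wording into the CRF completion guideline.

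SAP 1.3.1 reports enrolment in the past tense, so a protocol change may come too late to recover unrecorded events. If data collection is complete, state in the clinical study report which recording rule sites applied and that mild worsening of baseline symptoms may be under-counted. Protocol Appendix 7 lists the 9.3.1 sentence among the changes from version 6.3, so the report should also say whether practice changed then.

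The cost is a sentence or two of text and somewhat more mild AEs recorded in every arm, placebo included; after the fact, it is only the disclosure.
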